#### 12.4 Appendix 4: Patient Visit Schedule for Pharmacokinetic Sub-Study

**Day 0 : Patient Recruitment (Identification of patients who have previously had an ADR to a drug of interest or non-hypersensitive control patient).**

1. Consent	Written and verbal consent for inclusion into study
------------	---

Protocol V17 07.02.2023

2. Initial assessment	PMH/admission details  Current medications (including herbal and over the counter medications)  Alcohol/smoking/recreational drug use  Height/weight/ethnicity
-----------------------	--

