### 2.4.1 Case-Control Study

T-lymphocytes are thought to be involved in the pathogenesis of certain immunological drug reactions, causing tissue damage indirectly through the action of cytokines or directly by the secretion of cytolytic molecules. To stimulate a T-cell response a drug must act as an antigen and in some way ligate specific T-cell receptors. Despite this, the paucity of studies that define drug antigens has severely restricted mechanistic studies that relate the chemistry of antigen formation to immune function. In order to evaluate the relationship between hapten formation and the immune response, lymphocytes (T- and B-cells and other immune cell types) will be isolated from subjects with a history of hypersensitivity along with cells from appropriate non-hypersensitive control patients. Whole blood samples will be collected to:

Protocol V17 07.02.2023

- Characterise drug antigen-specific T-cell and B-cell responses
- Characterise the relative involvement of different T-cell populations
- Measure effector molecules secreted from stimulated T-cells (e.g., cytokines) and B-cells (antibodies)
- Quantify regulatory T-cell expression and activity
- Generate and characterize the phenotype and function of drug antigen specific T-cell clones.
- Generate B-cell lines and dendritic cells for use as antigen presenting cells in functional assays.
- Characterise an overall immunophenotype that occurs in response to therapy with oncological therapies (CPIs, targeted treatments and chemotherapy)
- Characterise the impact of changes to the microbiota on the immune system in the setting of adverse drug reactions
- Transcriptomics, HLA typing and single cell work will also be undertaken

All methods needed to complete the proposed experiments are established and performed routinely.

In addition, whole blood samples from cases and controls that are undergoing drug treatment will be collected and the hapten formed in plasma will be identified and quantified by mass spectrometry methods established in CDSS. This will allow us to evaluate the relationship between hapten formation and drug hypersensitivity.

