## **2.4.2 Cohort Studies**

### *2.4.2.1 Cohort Study – Drug Class NOS*

For each drug, and where appropriate, a small cohort of non-allergic control patients that are being administered the drug as part of their normal clinical care will be recruited to investigate the pharmacokinetics of hapten formation and clearance. Blood sampling will be detailed in section 5.

For each drug / chemical, or any drug class, we will aim to recruit no more than ten participants.

Currently, we have no plans to recruit participants under the age of 18 years to the cohort aspect of this study.

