**4.1.3 Cohort Study – Drug Class NOS**

*Inclusion Criteria for Cohort Studies*

- a. Subject is willing to take part
- b. 18 years or over
- c. Subject is willing to donate “pre-dose” blood sample(s) and follow specified sampling regime
- d. Subject is being administered the drug

*Exclusion Criteria for Cohort Studies*

- a. Unwilling to take part
- b. Subject is unable to consent
- c. Subject is, in the opinion of the Investigator, not suitable to participate in the study

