### ***5.1.1 Pharmacokinetic sub-study to investigate hapten formation and clearance***

The following outlines a detailed sampling procedure for the purpose of beta-lactam antibiotic hapten formation and clearance assessment. For other types of drugs, we would follow a similar procedure and ensure that no more than 20 samples (4mL per sample) are collected over 3 weeks.

- (a) Blood sampled in this sub-study will be collected into lithium/heparin coated vacuettes.
- (b) Blood will be sampled a maximum of 4 times a day; each blood sample will not exceed 4mL.

Protocol V17 07.02.2023

- (c) Sampling will be performed / defined on the basis of Cmax for the drug under study to enable blood to be sampled on the basis of peak and trough measurements of the free drug. Peak measurements will be taken 5 minutes after the drug had been administered intravenously; this will be in keeping with Tmax for drugs administered in this way.
- (d) Peak and trough blood sampling will be conducted twice a day for 2 days (i.e, 4 samples per day). For the following three days, blood sampling will be conducted to obtain two subsequent trough samples (i.e 2 samples per day) that will not exceed 4mL. Trough blood samples will be taken just before the administration of the next dose of drug.
- (e) After this initial 5-day period of blood sampling, blood will be sampled once a week for 3 weeks after the treatment has finished; the samples will not exceed 4mL. This is to measure the clearance of the drug-haptenated protein. During this time patients may have been discharged from hospital and, therefore, patients will be reimbursed reasonable travel expenses.
- (f) Plasma, required for bioanalysis, will be isolated within 60 minutes of each blood sample being taken, or as close as possible to this time point

Please note that on the basis of the initial assessments, participant availability and flexibility, we may change the sampling schedule but we will keep the total number of samples per patient constant. We will not exceed the total number of samples stated (seventeen samples (52 mls in total) over a four week period); however on occasion we may not obtain the full set of samples due to participant availability, withdrawal or Loss to Follow Up.

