## 12.2 Appendix 2: Patient Visit Schedule for Drug Class NOS studies

**Visit 1: Patient Recruitment (Identification of patients on active drug treatment either with or without evidence of ADR to drug).**

1. Consent	Written and verbal consent for inclusion into study
2. Blood sampling	Blood sample (up to 500mL) collected into a lithium/heparin / EDTA vacuette
3. Initial assessment	PMH/admission details  Current medications (including herbal and over the counter medications)  Alcohol/smoking/recreational drug use  Height/weight/ethnicity

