**Weeks 2-4: Single weekly blood samples**

1. Consent	Verbal consent for continuation in the study
2. Blood sampling	1 blood sample (4mL)

For patients taking oncological immunotherapies Plasma drug concentration samples will be taken prior to commencement of treatment, on the day of the initial treatment at Cmax, day 7, day 14 and day 21 of the initial treatment cycle. This is in keeping with the rest of the cohort schedule (Section 5.1.2.2.2) and will be taken at the same time.

[figure not shown]
Protocol V17 07.02.2023

**12.5 Appendix 5:** Flow chart for recruitment via direct healthcare professional referral

Protocol V17 07.02.2023

**12.6 Appendix 6:** Flow chart for recruitment from previous studies

Protocol V17 07.02.2023

[figure not shown]

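### The protocol gives two different populations and two different sampling anchors for the hapten pharmacokinetic sub-study

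*Protocol*

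**What the plan says.** **Population.** Section 2.4.2.1 sets up the cohort that investigates how haptens form and clear: "a small cohort of non-allergic control patients that are being administered the drug as part of their normal clinical care will be recruited". It caps this cohort at ten participants per drug. Appendix 4, the visit schedule to which 5.1.2.3 refers for this sub-study, opens with "Identification of patients who have previously had an ADR to a drug of interest or non-hypersensitive control patient". The only drug-related inclusion criterion in 4.1.3 is "Subject is being administered the drug". That list neither requires non-allergic status nor excludes a previous reaction.

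**Timing.** Section 5.1.1(e) says that after the first five days "blood will be sampled once a week for 3 weeks after the treatment has finished", and gives measurement of hapten clearance as the purpose. Appendix 4 heads the same three samples "Weeks 2-4: Single weekly blood samples" and does not mention the end of treatment. Section 5.1.1 also says that the whole set of seventeen samples falls within four weeks, and that a similar procedure will be used for drugs other than beta-lactams.

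**Related heading.** Appendix 2, the schedule for the Drug Class NOS studies, opens with "Identification of patients on active drug treatment either with or without evidence of ADR to drug". Section 2.4.1.1 also includes retrospectively identified cases and healthy volunteers who may never have taken the drug.

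**The concern.** A site needs one rule for who enters and one for when to draw blood. On entry, a site that follows 2.4.2.1 would turn away a patient with a previous reaction, and a site that follows Appendix 4 could enrol that patient. Nothing in the eligibility list settles the matter. With at most ten participants per drug, hapten kinetics could come from a mixture of prior reactors and tolerant patients whose make-up depends on which page each site read. It also bears on how the population is described to participants and the ethics committee.

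On timing, a clearance estimate needs samples taken after dosing has stopped. A sample drawn during treatment reflects formation and loss together. If the weekly samples are tied to calendar weeks, some of them can fall on treatment. Both schedules contain the same number of samples, so a completeness check on counts would not reveal this. Hapten clearance, and whether a threshold of hapten formation triggers an immune response, are stated study questions (2.2 and 3.4).

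**Working it through.** **Population, side by side**

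- Section 2.4.2.1: non-allergic patients already receiving the drug in routine care.
- Appendix 4: patients with a previous reaction to a drug of interest, or non-hypersensitive controls.
- Section 4.1.3: exposure to the drug, age, willingness and pre-dose sampling; silent on previous reactions.

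Appendix 4 admits everyone whom 2.4.2.1 admits, and adds prior reactors. The conflict concerns that added group only.

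**Sample count (the plan's own figure)**

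From 5.1.1(d) and (e): 4 per day × 2 days + 2 per day × 3 days + 1 per week × 3 weeks = 8 + 6 + 3 = 17. This reproduces the stated seventeen, and Appendix 4 gives the same total. The two schedules therefore differ in timing, not in number. (At the 4 mL maximum per sample, 17 × 4 = 68 mL, not the stated 52 mL. That is a separate discrepancy and plays no part here.)

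**Timing**

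Let D be the last treatment day, counting the first sampling day as day 1. The documents give no value for D, so a range of 5 to 28 is assumed.

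- 5.1.1(e): samples on days D+7, D+14 and D+21.
- Appendix 4: one sample in each of week 2 (days 8–14), week 3 (days 15–21) and week 4 (days 22–28). Days 14, 21 and 28 are assumed below.
- A sample counts as on treatment if its day is no later than D.

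| D | 5.1.1(e) sample days | Same weeks as Appendix 4? | 5.1.1(e) within 28 days? | Appendix 4 samples on treatment |
|---|---|---|---|---|
| 5 | 12, 19, 26 | yes | yes | 0 of 3 |
| 7 | 14, 21, 28 | yes | yes | 0 of 3 |
| 10 | 17, 24, 31 | no | no | 0 of 3 (1 of 3 if the week-2 sample is on day 8) |
| 14 | 21, 28, 35 | no | no | 1 of 3 |
| 21 | 28, 35, 42 | no | no | 2 of 3 |
| 28 | 35, 42, 49 | no | no | 3 of 3 |

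For D = 14, 21 and 28 the last column is the same whichever day of the week is used. The two rules agree only for D of about 5 to 7. Beyond that, Appendix 4 keeps to four weeks but starts to sample on treatment, while 5.1.1(e) samples after treatment but overruns four weeks (14 + 21 = day 35 > 28). So 5.1.1 also conflicts with itself for longer courses.

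**The case against.** Several points on the other side have force.

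- **Hapten measurement is not confined to tolerant patients.** Section 2.4.1 says that "whole blood samples from cases and controls that are undergoing drug treatment will be collected" for hapten quantification, and 3.4 plans hapten measurement over time without naming a population. Prior reactors in Appendix 4 may therefore be intended. That stands as a possible explanation. It does not remove the conflict, because 2.4.1 concerns the case-control study, while 2.4.2.1 defines the cohort for formation and clearance.
- **The two populations are not opposites.** A reader might take Appendix 4 to recruit reactors in place of tolerant patients. It does not: it admits both.
- **The headings may simply be loose.** A reader might infer that the Appendix 2 and Appendix 4 headings were swapped. The documents do not show this. The Appendix 2 heading fits prospective cases and Control group 1, and Appendix 3 uses wording close to that of Appendix 4, so reused text is just as likely.
- **The study gives no drug.** A reader might infer that the study re-exposes prior reactors. Under 2.4.2.1 dosing is routine care, and 5.4 says that participation does not alter care. Nothing supports a hazard caused by the study.
- **Reaction status is collected.** Appendix 7 records allergies, reaction details and re-challenge, so the groups can be separated. Mixing them would not by itself make the data uninterpretable.
- **The course lengths are assumed.** This is true. For a course that ends within the first week, Appendix 4 may be a fair summary of 5.1.1. Section 5.1.1 also lets the schedule change, but that clause holds the number of samples fixed and does not say which event the weekly samples are counted from.

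**Conclusion.** Both contradictions are in the current text and should be fixed. The first is one of scope: non-allergic patients only, against prior reactors as well, with no eligibility criterion to decide. The second is one of anchor: the end of treatment, against study weeks 2 to 4.

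The size of the timing problem depends on course length, which the protocol does not fix. It is nil for courses ending by about day 7. With samples assumed on days 14, 21 and 28, it reaches 1 of 3 clearance samples on treatment for a 14-day course and 3 of 3 for a 28-day course. The population problem cannot be given a number, because the documents do not say how many prior reactors would be enrolled; at most ten participants per drug are affected.

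This is a conflict between instructions in a small exploratory sub-study. The documents do not show which population or which anchor was intended, and this point takes no position on either.

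**What to change.** 1. Reconcile 2.4.2.1, 4.1.3 and Appendix 4 so that one population is stated, with a matching criterion on previous reactions in 4.1.3.
2. Reconcile 5.1.1(e), the four-week span in 5.1.1 and the weekly samples in Appendix 4, so that one anchor is stated and the span agrees with it for every course length expected.
3. Add the date and time of the last dose to the CRF. Appendix 7 lists dose and duration of treatment but not this. Each sample can then be classed as on or after treatment, and clearance analysed by time since last dose.
4. If prior reactors are intended, report them separately from tolerant patients, using the reaction data that the CRF already collects.
5. Check the Appendix 2 heading against the retrospective cases and healthy volunteers in 2.4.1.1.

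The cost is amendment wording and one CRF item. No extra samples or participants are needed.

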**Days 0/1-2: Preliminary Blood Samples**

1. Consent	Verbal consent for continuation in the study
2. Blood sampling	1 blood sample (4mL) immediately prior to drug dose = trough measurement
3. Blood sampling	1 blood sample (4mL) 5 minutes after drug dosing = peak measurement
4. Blood sampling	1 blood sample (4mL) immediately prior to subsequent drug dose = trough measurement
5. Blood sampling	1 blood sample (4mL) 5 minutes after drug dosing = peak measurement

**Days 3-5: Secondary Blood Samples**

1. Consent	Verbal consent for continuation in the study
2. Blood sampling	1 blood sample (4mL) immediately prior to drug dose = trough measurement
3. Blood sampling	1 blood sample (4mL) immediately prior to subsequent drug dose = trough measurement

[figure not shown]
**Weeks 2-4: Single weekly blood samples**

1. Consent	Verbal consent for continuation in the study
2. Blood sampling	1 blood sample (4mL)

For patients taking oncological immunotherapies Plasma drug concentration samples will be taken prior to commencement of treatment, on the day of the initial treatment at Cmax, day 7, day 14 and day 21 of the initial treatment cycle. This is in keeping with the rest of the cohort schedule (Section 5.1.2.2.2) and will be taken at the same time.

[figure not shown]
Protocol V17 07.02.2023

**12.5 Appendix 5:** Flow chart for recruitment via direct healthcare professional referral

Protocol V17 07.02.2023

**12.6 Appendix 6:** Flow chart for recruitment from previous studies

Protocol V17 07.02.2023

[figure not shown]
## 12.7 Appendix 7: Data to be collected in the CRF

- ❖ Date of Birth
- ❖ Weight (current and, if available, historical values including birth weight)
- ❖ Height (current and, if available, historical values)
- ❖ Past medical history including autoimmune disease
- ❖ Allergies
- ❖ Family history including allergies and autoimmune disease
- ❖ Smoking history (of older participants, and of home environment)
- ❖ Alcohol intake (of older participants)
- ❖ Ethnicity questionnaire
- ❖ Current medications
  - Dose
  - Duration of treatment
- ❖ Medications at time of reaction
  - Dose
  - Duration of treatment
- ❖ Other medications (herbal, over the counter, recreational)
  - Dose
  - Duration of treatment
- ❖ Information regarding drug reaction
  - Dose at time of reaction
  - Duration of treatment
  - If the drug/s was re-challenged
  - Recurrent reactions
  - Ongoing supportive therapy
- ❖ Clinical samples and investigational results
  - Haematological
  - Clinical Chemistry
  - Coagulation
  - Skin patch test
  - Biopsy

[figure not shown]

Protocol V17 07.02.2023

**12.8 Appendix 8:** Flow chart for recruitment via the Yellow Card Reporting System

[figure not shown]

**12.9 Appendix 9:** Flow chart for recruitment via industry partners

Protocol V17 07.02.2023

**12.10 Appendix 10:** Flow chart for recruitment via private healthcare providers

Protocol V17 07.02.2023

12.11 Appendix 11: **Flow chart for prospective cohort study for patients on treatments in oncology**

Procedures	Visit 1	Visit 2 (Up to 4 weeks)
	Informed consent	X
Demographics	X	
Medical history	X	
Punch biopsy (pre or post treatment)	X	X
Observation of treatment		X
40ml blood sample	X	X
DLQI	X	X

